## **10.7.** ADVERSE EVENTS DURING AT-HOME DOSING

The subject diaries will serve as source documentation for the collection of AEs occurring at home and these will be reviewed by the investigator, entered into the eCRF, and reported within the safety database. As for all AEs, these will be reported with a brief description of the at-home events, and their onset and resolution dates and times. The investigator will assess the severity of the AEs, their etiology (principally determining whether allergic or non-allergic), and their relatedness to study-product.

## **10.8. PREGNANCY TEST RESULTS**

Pregnancy test results will be listed by age group, treatment group, subject, and visit.

#### **10.9.** SPIROMETRY AND PEFR

Spirometry and/or Peak Expiratory Flow Rate (PEFR) assessments are performed prior to any DBPCFC. PEFR is also performed at each Up-dosing and Maintenance visit. Spirometry may be performed at any time during the study where a subject's pulmonary status is in question. Three attempts of FEV1 are performed, and the best (highest) value flagged in data listings. Similarly, three attempts of PEFR are performed, and the best (highest) value flagged in data listings. Only the best FEV1 value and the best PEFR value will be summarized. For analysis of FEV1/FVC ratio, the result corresponding to the best FEV1 value will be included in the applicable summaries.

Observed values for PEFR, FEV1, FEV1 percent predicted, FEV1/FVC ratio, and FEV1/FVC percent predicted as well as changes from baseline will be summarized at each applicable visit by treatment group for the Safety population. Results will be listed by age group, treatment group, subject, and visit.

#### 10.10. VITAL SIGNS

BMI will be calculated as (weight in kilograms)/ (height in meters).

Vital signs (pulse rate, systolic/diastolic blood pressure, body temperature, height, BMI, and weight) will be listed by subject and visit. Observed values and change from baseline will be summarized by treatment group at each scheduled visit and time point. At Screening and Exit DBPCFC vital signs are scheduled to be taken prior to each dose given. At Initial Escalation, Up-dosing, and Maintenance visits, vital signs are to be taken pre-dose and within 15-30 minutes after each dose given.

Additional vital signs measurements taken due to extension of the observation period will not be included in the summaries. If a subject is administered the same dose at more than one in-clinic visit (either the subject remained at the same dose as the previous visit, or a subject had a prior dose increase and subsequent dose reduction), an additional summary will be presented for that dose level (e.g., Up-dosing 3 mg Visit 2).

# **10.11. PHYSICAL EXAMINATION**

Physical examination results will be listed by age group, treatment group, subject, and visit. Results will be summarized by body system and treatment in a shift table of worst change from baseline that occurred within Up-dosing and Maintenance study periods, as well as overall.

Missing data will not be imputed.

The worst post-baseline result will be defined, within body system, as:

- Abnormal, clinically significant, if any clinically significant abnormal result is present after the first dose of randomized study treatment
- Abnormal, not clinically significant, if any abnormal, not clinically significant result is present after the first dose of randomized study treatment, but no clinically significant results
- Normal, if all non-missing results after the first dose of treatment are normal
- Not Done, if no results are present after the first dose of treatment

Population totals will be used as the denominator for all percentages.

#### **10.12.** ASSESSMENT OF ASTHMA CONTROL

Assessment of asthma control in asthmatic subjects using the Asthma Control Test (ACT) questionnaire will be performed at Baseline, Up-dosing Interim visit, End of Up-dosing Period visit, and Exit visit.

For subjects 12 years old or older, the ACT has 5 questions each recorded on a scale of 1 (worst control) to 5 (complete control). The total ACT is the sum of the 5 scores and ranges from 5 (worst control) to 25 (total control). A total score of 19 or less indicates asthma is not adequately controlled. Missing data will not be imputed. If any of the 5 questions have a missing response, the total ACT score will not be calculated.

For subjects under 12, there are 4 questions for the subject and 3 questions for the parents to complete. Subject responses range from 0 (worst control) to 3 (complete control). Parent responses range from 0 (every day) to 5 (no days). The sum of all 7 questions will make up the total score. The total ACT score for subjects under 12 will range from 0 (worst control) to 27 (worst control). Missing data will not be imputed. If any of the questions have a missing response, the total ACT score will not be calculated for that subject.

All analyses of the ACT will be performed separately by subject age group. Summary statistics of the score for question, total score and change from baseline will be tabulated by visit and treatment. A shift table of asthma control (adequate, not adequate, missing) will be summarized by treatment at each visit. The number of subjects with completed ACT questionnaires will be used as the denominator for all percentages.

Listing of the results from the questionnaire, including the total score, will be provided, sorted by age group, treatment group, subject, and visit.

# 10.13. ASSESSMENT OF GI SYMPTOMS BY PEESS

Subjects under the age of 18 who discontinue treatment due wholly or in part to GI AEs will be instructed to complete the Pediatric Eosinophilic Esophagitis Symptom Scores (PEESSTM v2.0) questionnaire (Franciosi, et al., 2011) monthly for 6 months.

The PEESS questionnaire is composed of 20 items investigating 2 domains. The total score consists of all 20 items. The frequency domain consists of items 1, 3, 5, 7, 9, 11, 13, 15, 17, 19, and 20, where each item is scored as: 0=Never, 1=Almost never, 2=Sometimes, 3=Often, 4=Almost always. The severity domain consists of items 2, 4, 6, 8, 10, 12, 14, 16, and 18, where each item is scored as: 0=Not bad at all, 1=A little bad, 2=Kind of bad, 3=Bad, 4=Very bad. Each item score is transformed to 0-100 as follows: 0=0, 1=25, 2=50, 3=75, 4=100.

The total and domain scores are computed as the sum of the items divided by the number of items answered. If more than 50% of the items for the calculation of the total score or either of the domain scores are missing, the score will not be calculated.

Summary statistics for the toal score and each PEESS domain will be tabulated by time point and treatment. PEESS results including the domain scores, will be listed.

# **10.14.** EPINEPHRINE USE AS RESCUE MEDICATION

Epinephrine use is defined as any rescue medication with a preferred name of 'EPINEPHRINE' when coded as described in Section 10.2, and with documentation of administration to a subject on a specific date.

All subjects, per protocol, are required to have epinephrine autoinjectors for use in case of a suspected anaphylactic reaction occurring outside of the clinic. There are, however, differences in how, and even if, physicians record the prescription of epinephrine autoinjectors for as-needed (PRN) use. As a consequence of this, the presence or absence

of a PRN prescription for epinephrine cannot be taken to indicate epinephrine usage, regardless of whether the prescription was written prior to, or after, enrollment in the study. What is important is to be able to quantitate the number of subjects receiving doses of epinephrine and the number of doses. As epinephrine should only be administered to treat a discrete allergic reaction, each dose of epinephrine should be closely temporally associated with a specific safety event and its use recorded on the Rescue Medication eCRF form. In cases where a PRN epinephrine prescription is issued after the start of study-product dosing, the sites will be queried as to if, and when, epinephrine was actually administered and to treat what specific event.

Epinephrine use will be categorized by the following period or events, based on epinephrine use on the same day(s) as any of the following events:

- Any use on the same date as an accidental exposure (defined as a recorded food allergy episode) occurring on or after the first dosing date of randomized treatment
- Screening DBPCFC, further categorized into
  - Peanut Challenge
  - Placebo Challenge
- Initial Escalation
- Up-dosing
- Maintenance
- Exit DBPCFC, further categorized into
  - Peanut Challenge
  - Placebo Challenge

If both peanut and placebo DBPCFCs were on the same date (either at Screening or Exit), any epinephrine use on that date will be categorized as used for the peanut challenge.

Frequency of use will be summarized overall (for any frequency) and by frequency administered (Once, twice, etc.). The number of subjects at risk at each time point will be used as the denominators; for instance, only subjects undergoing Exit DBPCFC will be used as the denominator for epinephrine use during Exit DBPCFC. The summary will be conducted in the Safety population. Data will be listed for all randomized subjects.

#### **10.15. ANAPHYLAXIS EPISODES**

All reported anaphylactic reaction episodes will be listed by age group, treatment group, and subject.

Each anaphylaxis reaction will be identified by the following triggers:

- DBPCFC
- Study drug

- Food allergen other than study drug while on treatment
- Non-food allergen while on treatment
- Other

Anaphylaxis reactions will be summarized in the Safety population separately for the following study periods:

- Screening DBPCFC, Peanut Challenge
- Screening DBPCFC, Placebo Challenge
- Overall Treatment Period (including Initial Escalation, Up-dosing, Maintenance)
- Initial Escalation
- Up-dosing
- Maintenance
- Exit DBPCFC, Peanut Challenge
- Exit DBPCFC, Placebo Challenge

For study periods of overall treatment period, Initial Escalation, Up-dosing, and Maintenance, additional summaries will be included by trigger (any trigger, study drug, food allergen other than study drug while on treatment, and non-food allergen while on treatment)

The number of anaphylactic reactions, the number and percent of subjects experiencing an anaphylactic reaction, the number and percent of subjects experiencing an anaphylactic reaction by maximum severity using the Murano Grading Scale (Muraro, et. Al), the number of subjects experiencing an anaphylactic reaction that was an SAE, the number of subjects experiencing an anaphylactic reaction that required use of epinephrine, and the number of subjects experiencing an anaphylactic reaction that involved individual symptoms will be summarized for each study period and trigger combination.

# 10.16. ALGORITHMIC SEARCH OF SYSTEMIC HYPERSENSITIVITY EVENTS

Systemic hypersensitivity events involving two or more body systems that occur together within a 2-hour window and not already determined as anaphylaxis events by the study investigators will be identified using Standard MedDRA Queries (SMQ) for Anaphylactic reaction AEs, hypotonic-hyporesponsive episode AEs, and selected sponsor-defined gastrointestinal AEs possibly associated with an allergic reaction to oral immunotherapy.

Systemic hypersensitivity cases must include the following categories or combination of categories (see below for categories' PTs):

- 1. Any term from category A or,
- 2. Any term from category D1 or,

- 3. Any term from category B and any term from categories C or D2 or E or,
- 4. Any term from category C and any term from categories D2 or E or,
- 5. Any term from categories D2 and any term from category E

Table of AE terms preferred terms:

Category	SMQ or Category Description	Preferred Term
A	Anaphylactic reaction (SMQ)	Anaphylactic reaction
		Anaphylactic shock
		Anaphylactic transfusion reaction
		Anaphylactoid reaction
		Anaphylactoid shock
		Circulatory collapse
		Dialysis membrane reaction
		Kounis syndrome
		Shock
		Shock symptom
		Type I hypersensitivity
В	Upper airway/respiratory AEs	Acute respiratory failure
2		Asthma
		Bronchial oedema
		Bronchospasm
		Cardio-respiratory distress
		Chest discomfort
		Choking
		Choking sensation
		Circumoral oedema
		Cough
		Cyanosis
		Dyspnoea
		Hyperventilation
		Dyspnoea
		Hyperventilation
		Irregular breathing
		Laryngeal dyspnoea
		Laryngeal oedema
		Laryngospasm
		Laryngotracheal oedema
		Mouth swelling
		Nasal obstruction
		Oedema mouth
		Oropharyngeal spasm
		Oropharyngeal swelling
		Respiratory arrest
		Respiratory distress
		Respiratory failure
		Reversible airways obstruction
		Sensation of foreign body
		Sneezing
		Stridor
		Swollen tongue
		Tachypnoea
		Throat tightness
		Tongue oedema

		Tracheal obstruction
		Tracheal oedema
		Upper airway obstruction
		Wheezing
С	Angioedema/urticaria/pruritus/flush AEs	Allergic oedema
U	Angioedema/urticaria/pruritus/ilusirAEs	Angioedema
		Erythema
		Eye oedema
		Eye pruritus
		Eye swelling
		Eyelid oedema
		Face oedema
		Flushing
		Generalised erythema
		Injection site urticaria
		Lip oedema
		Lip swelling
		Nodular rash
		Ocular hyperaemia
		Oedema
		Periorbital oedema
		Pruritus
		Pruritus allergic
		Pruritus generalised
		Rash
		Rash erythematous
		Rash generalised
		Rash pruritic
		Skin swelling
		Swelling
		Swelling face
		Urticaria
D1	Continues 1 m/h material AFr	Urticaria papular
D1	Cardiovascular/hypotension AEs	Blood pressure decreased
		Blood pressure diastolic decreased
		Blood pressure systolic decreased
		Cardiac arrest
		Cardio-respiratory arrest
		Cardiovascular insufficiency
		Diastolic hypotension
		Hypotension
D2	Hypotonic-hyporesponsive episode (SMQ)	Hypotonic-hyporesponsive episode
		Hypotonia
		Hypotonia neonatal
		Altered state of consciousness
		Depressed level of consciousness
		Hypokinesia
		Hypokinesia neonatal
		Hyporesponsive to stimuli
		Loss of consciousness
		Neurogenic shock
		Presyncope
		Shock
		Shock symptom Syncope

		Unresponsive to stimuli	
		Cyanosis	
		Cyanosis central	
		Cyanosis neonatal	
		Pallor	
		Skin discolouration	
Е	GI Related Symptoms	Abdominal discomfort	
		Abdominal pain	
		Abdominal pain upper	
		Diarrhoea	
		Enlarged uvula	
		Gastrointestinal disorder	
		Lip oedema	
		Lip pain	
		Lip pruritus	
		Lip swelling	
		Mouth swelling	
		Nausea	
		Odynophagia	
		Oral discomfort	
		Oral mucosal erythema	
		Oral pruritus	
		Paraesthesia oral	
		Retching	
		Saliva altered	
		Salivary hypersecretion	
		Swollen tongue	
		Tongue pruritus	
		Vomiting	

The following incidences will be summarized by treatment groups:

- Subjects with systemic hypersensitivity events that were:
  - Related to study drug
  - Related to study drug and led to study drug discontinuation
  - Serious
  - o Severe

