# **1.1. DOCUMENT HISTORY**

SAP Final Version 1 was approved prior to the first ARC003 subject unblinding (Dec2016). Updates for Version 2 of the SAP are being made post-unblinding of several subjects. It is important to note that all Aimmune and Agility Clinical, Inc. (Agility) staff involved in SAP development and study conduct responsibilities remain blinded to subjects' treatment assignments. The staff will remain blinded until the full study is unblinded post database lock.

Version 2 of the SAP incorporates feedback received by Aimmune from regulatory authorities on the ARC003 study protocol. The FDA correspondence was dated 13Jan2017 and notes the FDA's concern about the number of adult subjects in the study. Per the FDA, licensure of AR101 will likely be possible only in pediatric subjects ages 4-17 years. As such, the efficacy and safety endpoints have been modified in this version of the SAP and in the study protocol to note the primary population for analysis of all endpoints is in the pediatric population. The definition of EU primary and secondary endpoints were integrated in this SAP.

Other notable changes from Version 1 to Version 2 of the SAP include:

- The proportion of subjects aged 18 to 55 years who tolerate a single highest dose of at least 600 mg (for North America) and of at least 1000 mg (for EU) of peanut protein with no more than mild symptoms at the Exit DBPCFC was added as a key secondary efficacy endpoint.
- A tipping point sensitivity analysis of the primary efficiacy endpoint was added based on FDA feedback.
- The mITT population was removed as an analysis population since it was decided that sufficient sensistivity analyses of efficacy endpoints are defined in the SAP without including an mITT population.
- An SMQ search analysis of hypersensitivity events occurring with 2 hours of each other will be presented.
- Adverse event summaries combining adverse events collected on the adverse event page with including in-clinic dosing symptoms will be presented

Other changes have been made but do not materially alter analytical methods or planned summaries detailed in Final Version 1 of the SAP (dated 07Dec2016).

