- Subject incidence of TEAEs by MedDRA system organ class and preferred term;
- Exposure adjusted event rates for the most frequently-occurring TEAEs (i.e., TEAEs occurring in  $\geq$  5% of the Safety Population) by MedDRA preferred term;
- Subject incidence of TEAEs by severity grade, MedDRA system organ class, and preferred term;
- Subject incidence of TEAEs related to study drug by MedDRA system organ class, and preferred term;
- Exposure adjusted event rates for the most frequently-occurring TEAEs related to study drug (i.e., related TEAEs occurring in ≥ 5% of the Safety Population) by MedDRA preferred term;
- Subject incidence of ≥ grade 3 severity TEAEs related to study drug by MedDRA system organ class and preferred term;
- Subject incidence of SAEs by MedDRA system organ class and preferred term;
- Subject incidence of TEAEs leading to discontinuation of study drug by MedDRA system organ class and preferred term;
- Subject incidence of hypersensitivity TEAEs by MedDRA system organ class and preferred term, where hypersensitivity TEAEs are those TEAEs flagged as allergic reactions;
- Subject incidence of hypersensitivity TEAEs related to study drug by MedDRA system organ class and preferred term;
- Subject incidence of TEAEs associated with an accidental food allergen exposure by MedDRA system organ class and preferred term; and
- Subject incidence of TEAEs with onset < 90 minutes after study drug dosing by MedDRA system organ class and preferred term.

At each level of summarization (e.g., any AE, system organ class, and preferred term), subjects experiencing more than one TEAE will be counted only once within each study period. In the summary of TEAEs by severity grade, subjects will be counted once at the highest severity reported at each level of summarization.

Adverse event data will be presented in data listings by age group, treatment group, subject, study period, and event. Serious AEs; severe, life-threatening, or fatal adverse events; and AEs leading to discontinuation, reduction, or interruption of the study drug will be presented in separate data listings.

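### SAP 10.16: five preferred terms are listed in two categories that rules 3 and 4 pair, so, coded as numbered, one AE record can meet a rule meant to need two body systems

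*SAP*

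**What the plan says.** SAP 10.16 opens by describing its target as "Systemic hypersensitivity events involving two or more body systems that occur together within a 2-hour window", restricted to events that investigators have not already called anaphylaxis. The Document History (SAP 1.1) lists the search among the notable changes in Version 2: "An SMQ search analysis of hypersensitivity events occurring with 2 hours of each other will be presented".

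The operative part follows: "Systemic hypersensitivity cases must include the following categories or combination of categories". There are five rules. Rules 1 and 2 accept any single term from category A or D1. Rules 3 to 5 are pairings. Rule 3 is "Any term from category B and any term from categories C or D2 or E or", rule 4 is "Any term from category C and any term from categories D2 or E or", and rule 5 pairs D2 with E. A table then assigns preferred terms to A, B (airway/respiratory), C (angioedema, urticaria, pruritus, flush), D1, D2 (hypotonic-hyporesponsive) and E (gastrointestinal).

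The output is introduced by "The following incidences will be summarized by treatment groups". It counts subjects whose events were drug-related, drug-related and leading to discontinuation, serious, or severe.

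**The concern.** The opening definition needs two body systems and events that coincide. The pairing rules ask only whether a term from one category and a term from another are present. They do not say that the two must be different terms or different records, and nothing assigns a repeated term to one category. If a term is in both lists of a pairing, one record supplies both sides.

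The kind of event exposed to this is ordinary in the trial. Protocol 6.7.1 gives mild lip oedema as an example of a mild symptom. Protocol Appendix 3 groups swollen lips and tongue under skin/mucosal tissue and treats isolated skin or mucosal lesions after a food as a food-induced allergic reaction. An investigator would probably not call such an event anaphylaxis, so it would stay within this search. Coded literally, the search would report it as a systemic, two-system event.

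SAP 15 requires independent confirmatory programming. One programmer could flag categories, another could require two records, and each could cite 10.16.

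**Working it through.** **Inputs.** The term lists and rules 1 to 5 come from SAP 10.16. The plan gives no count to reproduce. One line in D2 runs Shock symptom and Syncope together; I read it as two terms merged in text extraction. Otherwise Shock symptom would drop out of the dual-listed set, and the five terms at issue would not change.

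**Step 1: distinct terms.** A 11, B 38 (40 printed lines, with Dyspnoea and Hyperventilation each printed twice), C 29, D1 8, D2 20, E 23. The sum is 129. Seven terms are in two lists and none is in three, so there are 129 − 7 = 122 distinct terms. In the categories used by rules 3 to 5 there are 38 + 29 + 20 + 23 = 110 entries, and 110 − 5 = 105 distinct terms.

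**Step 2: overlaps set against the rules.**

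| Term | Listed in | Paired by | One record qualifies as numbered? |
|---|---|---|---|
| Lip oedema | C, E | rule 4 | yes |
| Lip swelling | C, E | rule 4 | yes |
| Mouth swelling | B, E | rule 3 | yes |
| Swollen tongue | B, E | rule 3 | yes |
| Cyanosis | B, D2 | rule 3 | yes |
| Shock | A, D2 | none | yes, by rule 1 |
| Shock symptom | A, D2 | none | yes, by rule 1 |

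For example, "Swollen tongue" is in both B and E. Rule 3 needs B and one of C, D2 or E. With a single record B is true and E is true, so rule 3 is met. Rule 5 catches no single term, because D2 and E share none.

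**Step 3: every term as a lone record.** As numbered, 24 of the 122 terms qualify: 11 through rule 1, 8 through rule 2, and the five above through rules 3 and 4. The first 19 follow from how rules 1 and 2 are written. The five are 5/105 = 4.8% of the terms in B, C, D2 and E. That is a share of dictionary terms, not of events or subjects.

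**Step 4: the same run with two different records required in rules 3 to 5.** The five no longer qualify alone (5 before, 0 after). The 19 under rules 1 and 2 are unchanged.

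**Step 5: what two records do not settle.** A dual-listed term can still supply the second category beside a term that shares its first:

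- Lip swelling (C, E) with Urticaria (C), or with Lip oedema (C, E): rule 4.
- Swollen tongue (B, E) with Tongue oedema (B): rule 3.
- Mouth swelling (B, E) with Oropharyngeal swelling (B): rule 3.
- Cyanosis (B, D2) with Cyanosis central or Cyanosis neonatal (both D2): rule 3.

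**The case against.** The strongest reply is that the opening definition already excludes the feared case. A lone lip swelling coincides with nothing, and the listed combinations can be read as conditions within that definition, not as a replacement for it. A programmer who follows the lead-in would not count a single record. This stands: the over-count depends on coding the numbered rules literally. It does not dispose of the point, because the rules are what gets programmed and they omit the requirement.

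A second reply is that the effect is small. This largely stands. The output is descriptive. A subject is wrongly counted in a row only if a lone record of one of the five terms is that subject's only qualifying event for that row.

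A third is that requiring two records does not fully enforce two body systems. This also stands, as step 5 shows. Appendix 3 puts hives and swollen lips in one skin/mucosal group, so lip swelling with urticaria should not be presented as plainly two systems. Moving each dual-listed term to one category would address that, but it would also remove combinations such as swollen tongue with wheezing or, depending on the category chosen, cyanosis with dyspnoea or with loss of consciousness. That choice belongs to the sponsor.

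A reader might infer that the sponsor means to count single symptoms as systemic events, or that the table will be inflated in the AR101 arm. The documents support neither. The lead-in and the Document History both point to events occurring together, and no AE counts are given from which an excess or an arm difference could be derived.

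**Conclusion.** The rules in SAP 10.16 do not enforce the section's own definition for five named terms. Coded as numbered, one record of any of the five is a case, and subjects can be over-counted in this summary. The finding rests on the printed term lists and on literal coding of rules 3 and 4. Its measurable size is five self-qualifying terms. The number of subjects affected, and any difference between arms, cannot be computed.

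The point goes no further. Shock and Shock symptom are dual-listed but make no difference, because rule 1 accepts them alone. Acceptance of single A or D1 terms under rules 1 and 2 is a separate matter. No efficacy or other hypothesis test uses this search, and the investigator-reported anaphylaxis summary in SAP 10.15 is unaffected. It is a modest defect worth closing before lock, because a choice made after unblinding would be open to challenge.

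**What to change.** Add one sentence to rules 3 to 5 before database lock: a case requires at least two distinct AE records, with different preferred terms and onsets within 2 hours of each other, one record meeting each of the two paired categories, so that no single record can serve both sides. Leave the term lists and rules 1 and 2 as they are.

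State the limit next to it: pairs that share a category still qualify through the dual listing, such as those in step 5. The sponsor should decide by blinded review, before lock, whether such pairs count as two systems, and record the decision.

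The cost is one sentence, a small programming change and one item for the pre-lock review in SAP 11. Protocol 7.2 has sites record each symptom as its own AE, and SAP 10.7 has at-home AEs reported with onset times. The 2-hour window already in the section needs onset times in any case. SAP 10.16 does not say whether symptoms from in-clinic dosing, which are kept on a separate form, enter the search; if they do, the programmer should confirm that onset is held for each symptom.

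Lone occurrences on the AE page are not lost. They stay in the preferred-term tables of SAP 10.3, including the hypersensitivity table, "where hypersensitivity TEAEs are those TEAEs flagged as allergic reactions".
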